Sample Size and Rationale	Approximately 300 subjects : Re-enrollment is not allowed. - According to similar study results in the past, the difference between N-acetylcysteine (NAC) inhalation and standard treatment in the total score of the investigator's symptomatic severity assessment can be judged as 0.3. In this study, the assumed difference was 1 and the assumed standard deviation was 2.6, conservatively taking the highest value. With the assumed intraclass correlation coefficient (ICC) of 0.005, significance level of 5%, and test power of 80%, the study was to have 6 clusters (study centers) per treatment arm with a total of 12 clusters and 20 subjects in each cluster. it is calculated, as a result, that 120 subjects will be required per treatment arm and 240 subjects in total. Withdrawal is estimated at 20%; therefore, the plan is to recruit 300 subjects in total to have 150 subjects per arm and 25 subjects in each cluster.
Cluster (study center) Selection criteria	① Medical institutions in Korea at the general hospital level ② An otolaryngologist should be available to conduct the study.

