Eligibility Criteria – Inclusion Criteria	
 ① Patients are explained about the study objectives and methodologies, and shall express their consent by signing a written agreement for the use of their personal information. ② Male and female patients who are ≥ 18 years old. ③ Symptomatic acute rhinosinusitis patients whose symptoms have been present for more than 1 week and less than 12 weeks; recurrent acute rhinosinusitis patients (acute rhinosinusitis relapsed 3 times or more within 6 months, sub-clinical symptoms between the relapses); or, symptomatic acute-on-chronic (12 weeks or more) rhinosinusitis patients. 
 ➢ Patients display 2 or more symptoms that imply rhinosinusitis infection. The displayed symptoms should include at least one or more cardinal symptoms (nasal congestion or nasal/postnasal discharge). In addition, facial pain/sense of facial pressure, or reduction/loss of smell can also be accepted as relevant symptoms. ④ The total score of the investigator’s symptomatic severity assessment for a patient is 4 or above, and four symptomatic aspects (nasal congestion, nasal/postnasal discharge, facial pain/sense of facial pressure, reduction/loss of smell) are rated in four categories (0=no symptom, 1=mild, 2=moderate, 3=severe). ⑤ Patients have anterior rhinoscopy or nasal endoscopy results, and one or more of the following are observed: 
 ➢ Redness ➢ Edema or mucosal obstruction (mostly in the middle nasal) ➢ Mucopurulent discharge (mostly in the middle nasal) ➢ Nasal polyps
Eligibility Criteria – Exclusion Criteria	
 ① Patients with rhinosinusitis of dental origin. ② Patients with a known chronic pulmonary symptoms including bronchial asthma and chronic bronchitis. ③ Patients with nasal obstruction to the extent that drug administration is difficult. ④ Patients who have received endoscopic sinus surgery within the last 3 months. ⑤ Patients who have shown hypersensitivity or are likely to show hypersensitivity to N-acetylcysteine inhalation components (for the test sites) ⑥ Pregnant or breast-feeding patients. ⑦ Patients who are currently participating in other clinical trials (clinical trials for drugs or medical devices) or are planning to participate in other clinical trials during the duration of this study. ⑧ Patients who are not suitable for study participation upon the investigator’s judgment.

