Rhinosinusitis treatment	Patients are randomized to test sites and control sites at the cluster (study center) level. Study centers that are randomized as control sites apply standard treatments for rhinosinusitis excluding NAC inhalation, whereas study groups that are randomized as test sites apply NAC inhalation in addition to standard treatments for rhinosinusitis. This study is an observational study; therefore, the protocol does not present details of the standard treatments or NAC inhalation including dose per administration, number of doses, or administration methods. This study relies on the investigators’ daily medical practices and the patients’ conditions for appropriate decisions to be made. However, NAC can be diluted in sodium chloride or sterile distilled water and no other drugs (for example, bronchodilator) are to be mixed.
Study Methodology	<Overview>

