	
12 medical institutions in Korea that meet the inclusion criteria are cluster-randomized (test sites : control sites =1:1). Information about randomization is disclosed to both investigators and subjects. This means both study center investigators and subjects will be aware of the purpose of this study as well as the result of randomization (whether the subjects will receive NAC inhalation or not) from the beginning of the study.
 
Investigators shall obtain voluntary consent for participation in this research from patients who visit their medical institutions with symptomatic acute rhinosinusitis within the study duration. Patients who provided a written consent for the use of their personal information and who satisfy inclusion/exclusion criteria will be given a study enrollment number and available data on these patients will be collected among the predefined study relevant data in the case reports until Day 14 (± 3 days) from the starting day of treatment.
 
<Follow-up observation schedule and the scope of data collection>
 
Data created during subjects' visit to study centers for treatment shall be collected in the case report form. Follow-up observation time points defined below refer to data collection time points. That is, investigators can freely determine patient visit schedules based on the subjects' medical conditions regardless of the follow-up time points defined in this protocol. However, all the data created during the study period and judged to be necessary in relation to this study can be collected in the case report form.
 
In case of various tests including laboratory tests, no separate tests are conducted for this observational research and only those with test results are collected. Following data shall be collected during the study period.
 
 • Demographics of the subjects. • Disease information: diagnosis and start date of symptoms; indications on acute bacterial rhinosinusitis; anterior rhinoscopy/nasal endoscopy test results (for follow-up observation: if available); radiological test results (if available); and, infection source test results (if available). • Past medical history and intercurrent diseases: Examination on intercurrent diseases such as immune deficiency-inducing diseases, chronic diseases including diabetes, lower respiratory diseases, and asthma. Review on anatomical anomaly (if available) that increases the risk of rhinosinusitis, history of sinusitis surgery, and smoking preference. • Recent drug administration: Medication status for use of systemic antibiotics/antifungal agents, immunosuppressants, antihistamine drugs, or steroid for the past 4 weeks. • Body temperature, body weight, height (Enrollment data only for height and weight) • Rhinosinusitis treatment information: information on standard treatment and/or NAC inhalation, surgical procedures (if performed, for example: sinus irrigation or sinuscopy) • Co-medication/procedures: information on other drug administration and surgical procedures during the study period. • VAS assessment: to be indicated on 100mm VAS by subject for overall symptomatic severity. • SNOT-20 (Sino-Nasal Outcome Test) assessment: to be filled-out by subjects. • Investigator's symptom assessment: investigator's assessment for treatment response where each symptom's severity is rated by the investigator.

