Statistical Analysis Methods	
Analysis of primary endpoints
 
Obtain descriptive statistics (average, standard deviation, median, minimum, quartile, and maximum) for the change in the total score* of the investigator’s symptomatic severity assessment by treatment group on Day 14 compared with each time point and baseline (Day 0). Paired t-test shall be used to check intra-group change difference and Two sample t-test shall be used to check inter-group change difference.
 
Also, the same analytic methods shall be used for each cluster (study center).
 
Present ICC, and the Mixed model shall be used to check inter-group difference of the change in the total score of the investigator’s symptomatic severity assessment in consideration of clusters.
 
* The total sum of the investigator’s symptomatic assessment scores (on nasal congestion, nasal/postnasal discharge, facial pain/sense of facial pressure, and reduction/loss of smell).
 
Analysis of secondary endpoints
 
 Change in the total score of the investigator’s symptomatic severity assessment (Day 0, Day 7) Obtain descriptive statistics (average, standard deviation, median, minimum, quartile, and maximum) for the change in the total score of the investigator’s symptomatic severity assessment by treatment group on Day 7 compared with each time point and baseline (Day 0). Paired t-test shall be used to check intra-group change difference and Two sample t-test shall be used to check inter-group change difference.

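### Exclusion criterion 5 (NAC hypersensitivity) binds only the test sites, so written eligibility differs between arms for one subgroup: a minor comparability point, cheap to align and record

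*Combined protocol and SAP*

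**What the plan says.** All references are to the Synopsis in the combined protocol and SAP.

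- **Exclusion Criteria, item 5** excludes "Patients who have shown hypersensitivity or are likely to show hypersensitivity to N-acetylcysteine inhalation components (for the test sites". None of the other inclusion or exclusion criteria carries a site qualifier.
- **Exclusion Criteria, item 8** excludes "Patients who are not suitable for study participation upon the" investigator's judgment, at any site.
- **Rhinosinusitis treatment**: "Study centers that are randomized as control sites apply standard treatments for rhinosinusitis excluding NAC inhalation". Test sites add NAC inhalation to standard treatment.
- **Study Methodology, Overview**: allocation is open. "This means both study center investigators and subjects will be aware of the purpose of this study as well as the result of randomization" from the start. Consent and screening of individual patients follow.
- **Study Methodology, data to be collected**: hypersensitivity to NAC is not a named item. The medical history item is "Examination on intercurrent diseases such as immune deficiency-inducing diseases, chronic diseases including diabetes, lower respiratory diseases, and asthma", and the section adds that "all the data created during the study period and judged to be necessary in relation to this study can be collected", so the list is open-ended.
- **Statistical Analysis Methods, primary endpoint**: a two-sample t-test on the change in total score, and "the Mixed model shall be used to check inter-group difference of the change in the total score", allowing for clusters. Under the secondary endpoints, multiple regression on baseline factors is optional.

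**The concern.** In a cluster-randomized trial, randomizing the sites protects the comparison only if patients enter both arms under the same rules. Here one rule is applied after allocation is known, and in one arm only. Patients with shown or likely hypersensitivity are removed from the test arm but may remain in the control arm. Item 8 lets a control investigator exclude the same patient but does not require it.

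If these patients improve more or less than others on standard treatment, the control mean shifts and the between-arm difference in symptom change shifts with it. Neither primary analysis adjusts for who was eligible. Because the characteristic is not a named data item, these control patients may not be identifiable afterwards, and the sponsor might then be unable to show that the effect was nil. The 'likely' part of the criterion is also a judgement by staff who know the allocation, and only test sites are required to make it.

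**Working it through.** **Inputs from Sample Size and Rationale.** "In this study, the assumed difference was 1 and the assumed standard deviation was 2.6"; ICC 0.005; significance level 5% (taken as two-sided); power 80%; 6 clusters of 20 per arm, so 120 evaluable per arm; 20% withdrawal; 150 recruited per arm.

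**Inputs assumed, not in the documents.** p is the share of control subjects who meet criterion 5. D is the difference between their mean 14-day change and that of other control subjects (either sign).

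**Step 1: reproduce the plan's sample size.**
- Unadjusted n per arm = 2 × 2.6² × (1.960 + 0.842)² / 1² = 106.1.
- Design effect = 1 + (20 − 1) × 0.005 = 1.095.
- 106.1 × 1.095 = 116.2 per arm; 116.2 / 20 = 5.81 clusters, rounded up to 6, giving 120 per arm.
- 120 / (1 − 0.20) = 150 per arm, 300 in total. The stated figures reproduce.

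**Step 2: standard error of the between-arm difference.**
SE = √(2 × 2.6² / 120 × 1.095) = √0.12337 = 0.351.

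**Step 3: bias.** If other control subjects have mean change μ, the control mean is (1 − p)μ + p(μ + D) = μ + pD. The test arm has no such patients, so the difference is shifted by p × D in absolute size.

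**Step 4: two-sided type I error at that bias**, by the normal approximation and by a noncentral t on 10 df (12 clusters − 2):

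| p | D (points) | Bias (points) | Bias / SE | Type I error, normal | Type I error, t on 10 df |
|---|---|---|---|---|---|
| 1% | 1 | 0.01 | 0.03 | 5.0% | 5.0% |
| 1% | 2 | 0.02 | 0.06 | 5.0% | 5.0% |
| 5% | 1 | 0.05 | 0.14 | 5.2% | 5.2% |
| 5% | 2 | 0.10 | 0.28 | 5.9% | 5.8% |
| 10% | 2 | 0.20 | 0.57 | 8.8% | 8.1% |

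Type I error reaches 6% only at a bias of 0.103 points (normal) or about 0.114 points (10 df). At D = 1 that needs p of about 10% to 11%; at D = 2, about 5% to 6%.

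**Step 5: what aligning the wording alone would achieve in the broad case.** Suppose 10% meet the criterion, D = 2, and control sites exclude only a documented 1%. The remaining share is (0.10 − 0.01) / (1 − 0.01) = 9.1%, so the bias falls only from 0.20 to 0.18 points (type I error 8.1% normal, about 7.6% on 10 df).

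**Step 6: precision of a sensitivity analysis without these control patients.**
- At 1%: control n = 118.8 (19.8 per cluster), SE = 0.352, up 0.2%.
- At 10%: control n = 108 (18 per cluster), SE = 0.360, up 2.5%.

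**The case against.** The restriction has an evident reason. Control sites do not give NAC inhalation, so the exclusion has no safety role there, and the study is meant to reflect ordinary practice. This is not an internal contradiction. That stands, but it does not make the arms comparable for this subgroup, and applying the exclusion in both arms would not weaken its protection at test sites.

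The likely effect is negligible. This largely stands. The one row of the table with a sizeable effect needs 10% of control subjects to meet the criterion and a gap of 2 points, which is twice the planned difference and 2 / 2.6 = 0.77 of the assumed SD. Nothing in the documents points to such values. Exclusion criterion 2 also removes patients with known chronic pulmonary symptoms, including asthma, at all sites, which may shrink the subgroup equally in both arms; by how much is not stated.

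Aligned wording may not mean aligned practice. Control investigators have little reason to judge who is likely to react to a drug they do not give, and Step 5 shows how little the wording change then achieves. This stands, and it is why the exclusion counts are needed as well.

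The larger risk is recruitment by staff who know the allocation, with criterion 8 leaving room for judgement in either arm. This also stands; criterion 5 is a small, specific part of it.

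A reader might infer that the item goes unrecorded. The documents do not establish that: the data list is open-ended, only a synopsis is available, and a screening log or the full case report form may capture it. If one does, the sponsor can answer that part by citing it.

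**Conclusion.** The point holds as a minor one. Written eligibility differs between arms for patients with shown or likely hypersensitivity to NAC inhalation components, the rule operates after allocation is known, and the planned primary analysis does not correct for it.

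The size and direction of any bias are unknown because p and D are both assumed. If only documented cases count, put here at 1%, a gap of up to 2 points gives at most 0.02 points against an SE of 0.351 and leaves type I error at about 5.0%. A material effect would need both broad use of the 'likely' part at test sites and a large outcome gap.

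A reader might infer that the trial's comparison is biased or its type I error inflated to 8% or more. The documents do not support that: those figures come only from the far end of the assumed range. The case for acting is that the difference is avoidable at very little cost.

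**What to change.** **Preferred.** Delete the site qualifier so that criterion 5 applies in the same way at all 12 sites. At every site, record which screened patients are excluded under it, separately for shown and likely hypersensitivity, and report the counts by arm so that uneven use of the judgement part is visible.

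**If the restriction is kept.** State the reason, record criterion 5 status for every control subject, and prespecify a sensitivity analysis of the primary endpoint without those who meet it.

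**Cost.** One screening question at control sites, one tabulation, and no change to the planned sample size. With the preferred option, control sites lose about 150 × 0.01 = 1.5 of 150 patients at an assumed 1%, or 15 of 150 (2.5 per site) at an assumed 10%. The documents do not say whether these could be replaced; without replacement, the precision loss is that of Step 6. The sensitivity analysis would omit about 1.2 to 12 of 120 evaluable control subjects, with an SE of 0.352 to 0.360.

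**Limit.** Neither option removes selection by recruiters who know the allocation, and likely hypersensitivity remains an unblinded judgement.

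### Patients are recruited and scored for entry after the centre's arm is known, with no consecutive enrolment or screening log stated and no Day 0 adjustment in the primary analysis

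*Combined protocol and SAP*

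**What the plan says.** All of this is in the Protocol Synopsis.

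- **Study Methodology, Overview.** Twelve institutions are randomised 1:1. "Information about randomization is disclosed to both investigators and subjects", and both groups know the arm from the outset. Recruitment follows: "Investigators shall obtain voluntary consent for participation in this research from patients who visit their medical institutions with symptomatic acute rhinosinusitis within the study duration". The text gives no rule on the order in which patients are approached and mentions no record of eligible patients who are not enrolled.
- **Inclusion criterion 4.** The investigator's total score must be high enough: "symptomatic severity assessment for a patient is 4 or above". The total is the sum of four symptoms rated 0 to 3, so it runs from 0 to 12.
- **Exclusion criterion 8.** It leaves room for judgment: "Patients who are not suitable for study participation upon the investigator" finds unsuitable. No reasons are listed. Exclusion criterion 5 (hypersensitivity to NAC) is marked as applying to test sites only, so the written criteria already differ by arm.
- **Endpoints.** The primary endpoint is the Day 0 to Day 14 change in the same investigator-rated total.
- **Statistical Analysis Methods.** The arms are compared on change by a two-sample t-test and by a mixed model that takes account of centre. No patient-level covariate is named. Multiple regression is optional, sits under a secondary endpoint, and leaves its covariates to be chosen.

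**The concern.** Centre randomisation balances centres in expectation. It balances patients only if recruitment works the same way in both arms, and here every patient is identified, approached and scored after the arm is known. Each centre needs about 25 patients in about 18 months, or 25/18 = 1.4 a month, so there may be much room to choose whom to approach.

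The entry score is also the starting value of the primary endpoint. A difference between arms in how patients are picked, or in how Day 0 is scored, can therefore appear as a difference in change with no drug effect. Without a log, nobody could later tell whether recruitment differed by arm. The same section of the synopsis quotes a past difference of 0.3 points and plans on 1, so a bias of a few tenths would matter to the interpretation.

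**Working it through.** **Plan's own figure.** Inputs from Sample Size and Rationale: difference 1, SD 2.6, ICC 0.005, 5% (taken as two-sided), 80% power, 6 centres of 20 per arm.

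- Unclustered: 2 × (2.6 × (1.960 + 0.842)/1)² = 106.1 per arm.
- Design effect: 1 + 19 × 0.005 = 1.095, giving 116.2 per arm, or 5.8 centres, rounded up to 6. That is 120 per arm and 240 in total.
- Withdrawal: 240/0.8 = 300. The stated figures reproduce.
- Standard error of the difference: 2.6 × √(2 × 1.095/120) = 0.351. This takes 2.6 as the SD of the change, which the text does not specify.

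**Assumptions not in the documents.** Let D be the Day 0 gap (test minus control) and r the Day 0 to Day 14 correlation. SDs are equal at both days, so the slope of Day 14 on Day 0 equals r. There is no drug effect. The illustration uses D = 0.5 and r = 0.3 to 0.5.

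| How the gap arises | Day 14 gap | Bias in raw change | Bias after Day 0 adjustment |
|---|---|---|---|
| Selection on the observed Day 0 score | rD | (1 − r)D = 0.35 to 0.25, favouring NAC | rD − rD = 0 |
| All test-site entry scores rated up by 0.5 | 0 | D = 0.5, favouring NAC | rD = 0.15 to 0.25, favouring NAC |
| True severity gap, with r below 1 through rating noise | D | D − D = 0 | (1 − r)D = 0.35 to 0.25, against NAC |

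Simulation of the third row gave the same values.

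**A fourth mechanism: lifting scores only to reach the threshold.** Assume a Day 0 mean of 5 and a Day 14 mean of 3 before selection, SD 2, and every 3 rated as 4 at test sites only. In simulation the test-arm Day 0 mean falls by about 0.24, because patients at the minimum score are added. Change then moves against NAC by about 0.07 (r = 0.5) to 0.14 (r = 0.3).

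**Effect on the test.** Normal approximation, nominal two-sided 5%:

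- Bias 0.25: 0.25/0.351 = 0.71 standard errors, false-positive rate 11.0%.
- Bias 0.35: 0.35/0.351 = 1.00 standard errors, 16.9%.
- Bias 0.50: 0.50/0.351 = 1.42 standard errors, 29.6%.

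With a t reference on 10 degrees of freedom (12 centres), biases of 0.25 and 0.50 give 9.9% and 25%.

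**Range.** Bias in raw change, (1 − slope) × D, with false-positive rate, for selection on the observed score:

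| Day 0 gap D | Slope 0.25 | Slope 0.5 | Slope 0.75 |
|---|---|---|---|
| 0.25 | 0.19 (8.3%) | 0.125 (6.5%) | 0.06 (5.4%) |
| 0.5 | 0.375 (18.7%) | 0.25 (11.0%) | 0.125 (6.5%) |
| 1.0 | 0.75 (57%) | 0.50 (30%) | 0.25 (11%) |

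**Precision.** With equal SDs, the patient-level variance of adjusted Day 14 relative to raw change is (1 − r²)/(2(1 − r)) = (1 + r)/2, or 0.65 to 0.75 for r = 0.3 to 0.5. Adjustment is worth having even if recruitment turns out to be even.

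**The case against.** The strongest reply is that mechanism and direction are guesses. Both arms have the same target of 25 per centre and the same reason to reach 4, and the documents give no ground for expecting inflation at test sites only. Lifting a 3 to a 4 moves the result against NAC, and a true severity gap with rating noise leaves raw change unbiased while adjustment creates a bias. With a gap of 0.25, the false-positive rate is only 5.4% to 8.3%. All of that stands. It limits what can be claimed about size and direction, and it means that Day 0 adjustment alone is not a full remedy.

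The plan is also not bare. It requires symptom and endoscopic findings at entry, collects disease history, recent drugs, VAS and SNOT-20, and allows multiple regression, so measured imbalance could be examined. But that regression is optional, is not part of the primary analysis, and has no fixed covariates. None of these items shows who was eligible and not enrolled.

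Open label was a declared choice, and this point does not contest it. Nor does the observational label answer it: the study assigns centres to arms and tests between them, and a log adds no test, visit or treatment rule.

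Finally, the text is a synopsis, so the absence of a recruitment rule means that none is stated there. It speaks of investigators in general. That the same individual recruits and rates is the natural reading, since no independent assessor is named, but it is not stated.

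**Conclusion.** The design leaves patient selection and entry scoring open to knowledge of the arm. The stated plan has neither a recruitment safeguard nor a prespecified Day 0 adjustment in the primary analysis. This should be changed.

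Under the illustrated selection on the observed score, the bias in raw change is 0.25 to 0.35 points, 0.7 to 1.0 standard errors. It is 0.5 if every test-site entry score is rated up by 0.5. These sizes rest on an assumed 0.5-point gap, r of 0.3 to 0.5, equal SDs and no drug effect.

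A reader might infer that recruitment differences pass in full into the primary result and favour NAC. The documents do not support that: a change score subtracts Day 0, so the share carried over depends on how the gap arose and can be zero or reversed. A reader might also infer that adjusting for Day 0 settles the matter. It does so only when selection acts through the observed score, and it does not correct unmeasured prognosis.

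**What to change.** 1. **Study Methodology, Overview.** Require each centre to approach consecutive eligible patients up to its quota. Each centre keeps an anonymous log of patients seen, eligible, approached and consented, with the reason for non-enrolment, including use of exclusion criterion 8. Summarise the log by arm together with the distribution of Day 0 total scores, so that a difference in case mix or a cluster of scores at 4 can be seen.
2. **Statistical Analysis Methods, primary endpoint.** Make the primary between-arm analysis a mixed model of the Day 14 total score, with the Day 0 total score as covariate and centre as a random effect. Report the unadjusted mixed model of change as a sensitivity analysis. If the two disagree, read them against the log and the Day 0 distributions, because each is unbiased under a different account of the gap.

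Cost: protocol and SAP wording, a few minutes of site work per screened patient, and one additional analysis. No extra patients, visits or assessors are needed.

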--	--

	
 Existence of rhinosinusitis complications. Adverse drug reaction related to NAC inhalation. Serious adverse events /adverse drug reactions.
Endpoints	
Primary Endpoint
 
 Change in the total score of the investigator’s symptomatic severity assessment (Day 0, Day 14) (Assessed symptoms: nasal congestion, nasal/postnasal discharge, facial pain/sense of facial pressure, reduction/loss of smell are rated in four categories [0=no symptom, 1=mild, 2=moderate, 3=severe]) 
Secondary Endpoint
 
 Change in the total score of the investigator’s symptomatic severity assessment (Day 0, Day 7) Change in the score of the investigator’s symptomatic severity assessment (Day 0, Day 7, Day 14) Change in SNOT-20 score (Day 0, Day 14) 
Safety Assessment Parameters
 
 Adverse drug reaction (ADR) related to NAC inhalation and incidences/profiles of serious adverse events and ADRs. Rate of subjects who discontinued the study due to ADR and relevant ADR profiles.

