	
If necessary, in addition, Repeated Measures ANOVA can be conducted to check inter-group difference taking into account of changes in the total score of the investigator's symptomatic severity assessment on baseline (Day 0), Day 7 and Day 14. Multiple regression analysis can also be performed to check factors that influence the change in the total score of the investigator's symptomatic severity assessment. For this, independent parameters may include demographics, baseline characteristics and clinical factors that can be selected in consideration of collected data or clinical characteristics.
 
 • Change in SNOT-20 scores (Day 0, Day 14) Obtain descriptive statistics (average, standard deviation, median, minimum, quartile, and maximum) for individual and total SNOT-20 scores by group on Day 14 compared with each time point and baseline (Day 0). Paired t-test shall be used to check intra-group change difference and Two sample t-test shall be used to check inter-group change difference. 
Analyses of safety data
 
 • Adverse drug reaction (ADR) incidence Present the number of subjects with ADR related to NAC inhalation, ADR incidence, 95% confidence interval for the incidence, and the number of ADR cases. Also, present the number of ADR cases by characteristic (severity, measures taken, progress, and etc.) • Serious adverse event/adverse drug reaction incidence Present the number of subjects with serious adverse event(s) and serious adverse drug reaction(s), their incidence, 95% confidence interval for the incidence, and the number of cases.
--	---

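### The planned between-group test for the Day 7 total score and SNOT-20 ignores the cluster randomisation, and for the primary endpoint the same t-test stands unranked beside the mixed model

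*Combined protocol and SAP*

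**What the plan says.** All references are to the protocol synopsis.

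- **Design** (Study Methodology, Overview): "12 medical institutions in Korea that meet the inclusion criteria are cluster-randomized", in a 1:1 ratio. Each centre therefore contributes to one arm only.
- **Sample size** (Sample Size and Rationale): six centres per arm with 20 patients each, difference 1, SD 2.6, power 80%. Clustering is allowed for: "With the assumed intraclass correlation coefficient (ICC) of 0.005".
- **Primary endpoint** (Analysis of primary endpoints): two between-group tests are both required. One is "Two sample t-test shall be used to check inter-group change difference". The other is "Present ICC, and the Mixed model shall be used to check inter-group difference", described as taking clusters into account. Neither is named as the deciding one.
- **By-centre analysis** (same place): "Also, the same analytic methods shall be used for each cluster (study center)".
- **Day 7 total score and SNOT-20** (Analysis of secondary endpoints): the t-test sentence is repeated for each, and the mixed model is not. For the total score, "Repeated Measures ANOVA can be conducted to check inter-group difference" if thought necessary, and a multiple regression is also optional. Neither mentions a centre term.
- **Third secondary endpoint** (Endpoints): change in the score of the investigator's "symptomatic severity assessment (Day 0, Day 7, Day 14)". It has no entry of its own in the analysis text.

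**The concern.** A two-sample t-test on patients takes its standard error from the spread between patients and assumes that they are independent. When whole centres are allocated, any difference between centres adds variance to the arm comparison that this standard error does not contain. The test then rejects too often.

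For the Day 7 total score and SNOT-20, no firmly planned test corrects this. For the primary endpoint a suitable model is planned, but two required tests of the same difference can disagree, and the result could be read from whichever is more favourable. Presenting the ICC does not correct any p-value.

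The by-centre instruction also fails in part. Descriptive statistics and the paired t-test can be run within a centre. A between-group test cannot, because each centre has one arm.

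**Working it through.** **Inputs** (Sample Size and Rationale): k = 6 centres per arm; m = 20 evaluable per centre, or 25 if nobody withdraws; difference 1; SD 2.6; ICC 0.005; significance level 5%, taken as two-sided because the sidedness is not stated. The larger ICCs below are assumptions and are not in the documents.

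**1. The plan's own sample size.**
- Independent patients: 2 × (2.6 × (1.960 + 0.842))² / 1² = 106.1, so 107 per arm.
- Design effect: DE = 1 + (m − 1) × ICC = 1 + 19 × 0.005 = 1.095.
- 107 × 1.095 = 117.2, so 118 per arm, or 5.9 centres of 20. Rounded up to 6 centres, this is 120 per arm and 240 in total.
- Withdrawal: 240 / 0.80 = 300.

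The stated figures reproduce. The sizing uses a design effect that the patient-level t-test leaves out.

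**2. Type I error of the patient-level t-test.** The true standard error is √DE times the one that the test uses, so the true error rate is about 2 × (1 − Φ(1.96 / √DE)). At ICC 0.005 and m = 20: √1.095 = 1.046; 1.96 / 1.046 = 1.873; the rate is 6.1%.

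| ICC | DE, m = 20 | Type I error | DE, m = 25 | Type I error |
|---|---|---|---|---|
| 0.005 (plan) | 1.095 | 6.1% | 1.12 | 6.4% |
| 0.02 (assumed) | 1.38 | 9.5% | 1.48 | 10.7% |
| 0.05 (assumed) | 1.95 | 16.0% | 2.20 | 18.6% |
| 0.10 (assumed) | 2.90 | 25.0% | 3.40 | 28.8% |

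One million draws from the exact sampling distribution, with 6 + 6 centres, agree to within 0.3 percentage points. A t-test on the 12 centre means (10 df) holds 5%; in simulations of 20,000 trials per setting it ranged from 4.6% to 5.2%.

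**3. Standard error, m = 20.** The t-test's standard error is too small by 1 − 1/1.046 = 4.4% at ICC 0.005, and by 1 − 1/1.396 = 28.4% at ICC 0.05.

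**4. Power of a test with the right degrees of freedom, ICC 0.005.** SE = 2.6 × √(2 × DE / (k × m)).
- k = 6, m = 20: SE = 2.6 × √(2 × 1.095 / 120) = 0.351 and 1/SE = 2.847. The normal approximation gives Φ(2.847 − 1.960) = 81.2%. The noncentral t with 10 df (critical value 2.228) gives 72.8%.
- k = 6, m = 25: SE = 2.6 × √(2 × 1.12 / 150) = 0.318. Power on 10 df is 80.9%.
- k = 7, m = 20: SE = 2.6 × √(2 × 1.095 / 140) = 0.325. Power on 12 df is 80.6%.

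**5. How often the centre variance is estimated as zero.** This happens when the between-centre mean square (10 df) does not exceed the within-centre mean square (12 × 19 = 228 df). Their expected ratio is 1.095 / 0.995 = 1.101. P(F with 10 and 228 df ≤ 1/1.101) = 47%.

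**The case against.** The strongest reply is that the primary endpoint already has a required model that allows for centres, and that at the plan's own ICC the excess for the other endpoints is only 1.1 to 1.4 percentage points. Both statements are true. For the primary endpoint the fault is a missing ranking, not a missing adjustment. The large error rates all rest on assumed ICCs. However, the documents give no source for 0.005. They also leave treatment details and visit timing to each investigator, and they have unblinded investigators score the primary endpoint. Differences between centres are therefore plausible.

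Four points about the reading also stand as qualifications:

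- The unit of the t-test is not named. That it is the patient is inferred, because only the mixed model is said to consider clusters and centre means are never mentioned.
- The mixed-model sentence gives no day, so Day 7 is not strictly excluded. It stands under the primary heading and is not repeated. On any reading it does not cover SNOT-20.
- The ICC of 0.005 was set when sizing the trial on the investigator's total score. Applying it to the patient-completed SNOT-20 is an assumption.
- The third secondary endpoint omits the word total, which suggests the separate symptom scores, but the text does not say so. It could mean the total score over the three time points, which the optional repeated-measures analysis would address.

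None of these supplies a firmly planned test for SNOT-20 that allows for centres, or a rule for which primary test decides.

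**Conclusion.** The concern holds and should be fixed. As written, SNOT-20 and, on the natural reading, the Day 7 total score are compared by a test that does not respect the unit of randomisation, and the primary endpoint has two required tests with no order between them.

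The excess false-positive rate is small if the ICC is 0.005 for these outcomes (6.1% to 6.4% instead of 5%) and grows quickly if it is larger. The calculations assume equal centre sizes, normal data, a two-sided test and a patient-level t-test. For SNOT-20 the claim needs only an ICC above zero; its size there is not known from the documents. No confidence interval for efficacy is planned, but one derived from the t-test would be too narrow on the same grounds.

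**What to change.** - **Primary endpoint:** name the mixed model with a random centre intercept and a small-sample correction of the degrees of freedom, such as Kenward-Roger, as the sole inferential between-group analysis.
- **Zero centre variance:** state in advance what is done then, for example the t-test on the 12 centre means with 10 df. At the plan's ICC this would arise in nearly half of trials.
- **Secondary endpoints:** use the same approach for the Day 7 total score and SNOT-20. State what the third secondary endpoint is, and use the same approach for any between-group test of it.
- **Optional models:** include a centre effect in any repeated-measures or regression analysis.
- **Patient-level two-sample t-tests:** label them descriptive.
- **By-centre output:** limit it to descriptive statistics and change within the centre.
- **Power:** restate it on the degrees of freedom of the chosen test.

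The cost is analysis-plan wording and a few lines of code; no new data are needed. P-values become less favourable on average, though not in every dataset. The restated power is 72.8% with 20 evaluable patients per centre and passes 80% only if all 25 recruited per centre are evaluable. Seven centres per arm would also reach 80% with 20 each, but the fix does not require more centres: reporting the power correctly is enough.
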